8.4.4 Electrocardiogram (ECG)

Twelve-lead safety ECGs are collected at the study site using ECG equipment available at the sites. This ECG must be read on site by a qualified physician (e.g., the investigator, or another qualified physician such as a consulting cardiologist) on the day they are collected and recorded in eCRF for each patient.

Only ECGs with clinically significant ("notable") abnormalities should be reported as AE. A "notable abnormality" is defined as:

- QTcF > 480msec with acute cardiovascular risk, as assessed by a consulting cardiologist
- Any QTcF > 500msec, confirmed by a consulting cardiologist

- QTcF increase > 60 msec from baseline.

The frequency of the ECG assessment is provided in [Table 8-1](#).

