## 5.3 DATA FROM PARENT STUDIES

Data referring to the disease history, as well as the height, were not collected in the study EDC but remained in the databases of the parent studies where the patients are coming from.

In addition, the data from the end of the treatment (or last visit) in the parent studies, will be extracted by the parent studies databases and transferred by the sponsor to the CRO. The date of the EOT visit from the parent study will be matched with the date of the baseline (W1D1) to guarantee the proper correspondence. The cases with a discrepancy exceeding one week between the two dates will be evaluated case by case.

For disease history they are the following ones:

- Time (months) to first study osilodrostat dose since diagnosis
- Classification at time of diagnosis
- Cushing's Disease Status
- Any previous surgery
- Any previous, non-LCI, treatments for Cushing's disease
- Any previous pituitary irradiation
- Baseline mean UFC.

---

Study Code: CLCI699C2X01B

---

For W1D1 visit the data to be transferred will regard the following topics:

- Vital signs (domain VS)
- ECG (domain EG)
- MRI (domains PR, FA)
- Laboratory (domain LB)

The data will be extracted as SAS datasets as close as possible to the domain structures reported in attachment 8.2.

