#### 7.4.4 Weight on treatment: Increase $>=10\%$ / Decrease $>=5\%$ ECG

ECG data will be summarized with:

- shift table baseline to worst on-treatment result for overall assessments
- number and percentage of patients with clinically notable abnormalities will be summarized
- listing of ECG evaluations for all patients with at least one abnormality.

A "notable abnormality" is defined as:

For PR are:

---

---

Study Code: CLCI699C2X01B

- > 200 ms post-baseline and  $\leq$  200 ms at baseline
- Increase > 25% compared to baseline to a post-baseline value > 200 ms

For QRS are:

- > 110 ms post-baseline and  $\leq$  110 ms at baseline
- Increase > 25% compared to baseline to a post-baseline value > 110 ms

For QT and QTcF are:

- > 450 ms at any post-baseline and  $\leq$  450 ms at baseline
- > 480 ms at any post-baseline and  $\leq$  480 ms at baseline
- > 500 ms at any post-baseline and  $\leq$  500 ms at baseline
- an increase from baseline > 30 ms at any post-baseline
- an increase from baseline > 60 ms at any post-baseline

For HR are:

- Increase > 25% and HR > 100 bpm
- Decrease > 25% and HR < 50 bpm

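### The SAP 7.4.4 rows for QTcF above 450, 480 and 500 ms count only newly exceeded limits against an on-drug baseline, and no table counts patients above each limit regardless of baseline

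*SAP*

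**What the plan says.** SAP 7.4.4 states that the "number and percentage of patients with clinically notable abnormalities will be summarized". For QT and QTcF it lists five criteria:

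- three absolute limits, "> 450 ms at any post-baseline and", "> 480 ms at any post-baseline and" and "> 500 ms at any post-baseline and", each completed by the condition that baseline is at or below the same limit;
- two changes, "an increase from baseline > 30 ms at any post-baseline" and "an increase from baseline > 60 ms at any post-baseline", with no condition on the baseline level.

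The section also plans a baseline-to-worst shift table of the overall ECG assessment and a listing of ECGs for patients with at least one abnormality. It has no rule for a missing baseline ECG.

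SAP 4.1.1 sets baseline as the End of Treatment visit of the parent study. SAP 5.3 has those ECG data transferred from the parent databases and the visit dates matched: "The cases with a discrepancy exceeding one week between the two dates will be evaluated case by case".

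Protocol 8.4.4 defines the notable ECGs to be reported as adverse events. One criterion is "Any QTcF > 500msec, confirmed by a consulting cardiologist". The others are QTcF above 480 ms with acute cardiovascular risk, and a rise above 60 ms.

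For laboratory grades, SAP 7.4.2 includes a worst post-baseline count that disregards baseline status.

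**The concern.** QT prolongation is named as a known risk in Protocol 4.5, is an adverse event of special interest in SAP 8.1, and has its own discontinuation criteria in Protocol 9.1.1. A reader of the ECG table will want to know how many patients were above 450, 480 or 500 ms during long-term treatment. The planned rows answer a different question: how many moved above the limit after a baseline at or below it.

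That convention suits a pre-treatment baseline, where a high value is background. Here the baseline is taken on drug, so a high value may already reflect treatment, and the condition then removes a patient of interest. Protocol 5.1 and 5.2 set no QTcF limit for entry, so a baseline above 450 or 480 ms is possible.

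At 500 ms the SAP and Protocol 8.4.4 use the same term, notable abnormality, for different sets of patients.

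**Working it through.** **Step 1. Apply the five criteria to single cases.** With baseline b and a post-baseline value p, limit row L is met if p > L and b ≤ L. The change rows are met if p − b > 30 or p − b > 60.

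| Baseline (ms) | Post-baseline (ms) | SAP QTcF rows met | Above 500 ms |
|---|---|---|---|
| 440 | 505 | >450, >480, >500, rise >30, rise >60 | yes |
| 490 | 505 | >500 | yes |
| 505 | 505 | none | yes |
| 505 | 530 | none | yes |
| 505 | 536 | rise >30 | yes |
| 505 | 570 | rise >30, rise >60 | yes |
| 485 | 495 | none | no |
| missing | 505 | none | yes |

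Over a 1 ms grid (baseline 380 to 560, post-baseline to 600), a patient with a recorded baseline above a limit escapes all five criteria exactly when the rise is at most 30 ms and no higher limit is crossed. With a missing baseline every criterion fails, because each one refers to baseline.

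**Step 2. Compare with Protocol 8.4.4.** At 500 ms the protocol requires cardiologist confirmation but sets no baseline condition, so the SAP row is narrower on baseline. At 480 ms the protocol also requires acute cardiovascular risk, so the two are not like for like. The protocol has no 450 ms limit. Its rise above 60 ms needs a baseline, as the SAP's does.

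**Step 3. Illustrative size.** The plan states no figure to reproduce and gives no QTcF distribution. Everything here is assumed: patient means normal with mean 420 ms and SD 20 ms, within-patient SD 12 ms, the same mean at baseline and later (both on drug), and k = 10 post-baseline ECGs. Protocol 4.5 schedules ECGs every 24 weeks, so 10 ECGs span 240 weeks, close to the planned five years.

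Write Φ_L(m) = Φ((L − m)/12) and average over m:

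- any value above L: E[1 − Φ_L(m)^10]
- counted in the SAP row: E[(1 − Φ_L(m)^10) × Φ_L(m)]

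| Limit | Any value above | Counted in row | Omitted, per 100 patients | Omitted share of those above | In no QTcF row |
|---|---|---|---|---|---|
| 450 ms | 29.25% | 20.24% | 9.0 | 9.02/29.25 = 31% | 25% |
| 480 ms | 2.55% | 2.19% | 0.36 | 0.364/2.549 = 14% | 11% |
| 500 ms | 0.198% | 0.182% | 0.016 | 0.0164/0.198 = 8% | 8% |

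These come from numerical integration. At 500 ms a simulation of 400,000 patients would contain about 0.00198 × 400,000 = 792 patients above the limit, so its omitted share has a standard error of √(0.083 × 0.917/792) ≈ 1 percentage point. A simulated 9% agrees with 8%.

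Varying the mean over 415 to 425 ms, the SDs over 18 to 20 and 10 to 12 ms, and k over 6 to 10, the share omitted from the row is 23 to 43% at 450 ms, 9 to 23% at 480 ms and 5 to 14% at 500 ms.

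If a fraction f of patients had no baseline ECG, independently of QTcF, each row's remaining count would be multiplied by 1 − f. The documents do not give f.

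**The case against.** The strongest reply is that this is an ordinary newly-occurring convention, used consistently. PR and QRS in SAP 7.4.4 have the same form, and adverse events are counted as new or worsening from baseline. The study is descriptive, and the ECGs in question have other outlets: the listing, the shift table, adverse events leading to discontinuation, and the special-interest group for QT prolongation, which has no baseline-ECG condition. Management under Protocol 6.5.1.2 and 9.1.1 also makes a roll-over patient with a confirmed baseline above 500 ms unlikely.

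Much of this stands, and it rules out four stronger readings that a reader might infer:

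- *High-baseline patients are never counted.* They can enter a change row or a higher-limit row (505 to 536 ms, or 490 to 505 ms).
- *The SAP contradicts the protocol at all three limits.* The comparison is direct only at 500 ms, and Protocol 8.4.4 governs adverse event reporting without prescribing a table.
- *Baseline ECGs are known to be missing.* The ECG is scheduled at baseline, and SAP 5.3 says that date discrepancies are evaluated, not that values are dropped. Missing baselines are a possibility of unknown frequency.
- *The table cannot be reconciled with QT discontinuations because of this rule.* Those depend on cardiologist confirmation or investigator judgement, so unconditional rows would not match them one for one either. They are traced through disposition and adverse events leading to discontinuation.

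The other outlets still do not supply the missing number. Adverse event tables count preferred terms, not millisecond limits, and Protocol 10.1.1 sends conditions already present at consent to medical history. The shift table covers only the overall assessment. The listing is not a count, and SAP 7.4.4 does not say whether its abnormality criterion is the notable definition that follows it.

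**Conclusion.** The point holds in this limited form and is minor. The three limit rows measure newly exceeded limits against an on-drug baseline. A patient above a limit at baseline who rises by at most 30 ms and crosses no higher limit, or any patient without a baseline ECG, is in no QTcF notable count. At 500 ms the SAP definition is narrower than the protocol's.

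The size cannot be established from the documents. In the assumed scenario about 31%, 14% and 8 to 9% of patients exceeding 450, 480 and 500 ms are omitted from the row. About 25%, 11% and 8 to 9% are in no QTcF row at all. In absolute terms the omission is mainly at 450 ms, which plays no part in the protocol's notable or discontinuation criteria; at 500 ms it is about 0.02 per 100 patients. The scenario ignores dose interruption and discontinuation for QT prolongation.

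**What to change.** In SAP 7.4.4:

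1. Keep the present 450, 480 and 500 ms rows and label them *newly occurring*.
2. Add the number and percentage of patients with any on-treatment QTcF above 450, 480 and 500 ms regardless of baseline, including patients whose baseline is missing. This follows the approach of SAP 7.4.2 for laboratory grades.
3. Report the number of patients without a baseline ECG, and state that they cannot contribute to the newly occurring or change rows.

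The cost is three table rows and one count from data already collected. Reported QTcF counts will be slightly higher, and the labels must make clear that the added rows include values already high at baseline.

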#### 7.4.5 Tumor volume and longest dimension

For tumor volume evaluated by MRI scanning, descriptive summary of actual tumor volumes as well as its change from baseline will be provided at visits where evaluation is scheduled. For MRI images (or CT) that are not interpretable for tumor volume, the longest dimension (in mm) will be summarized instead. Due to evaluation schedule, this analysis will only be performed for the overall study period.

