Known risks of treatment with LCI699 in patients with CS include: QT prolongation, hypocortisolism/adrenal insufficiency, AEs related to the accumulation of precursor molecules, including: increased or decreased blood pressure, hypokalemia or hyperkalemia, hyponatremia, weight gain, edema, and increase in the synthesis of sex steroids (primarily adrenal androgens in women) that may lead to menstrual changes and hirsutism in women and acne in either men or women. Skin rash has been observed. Corticotroph tumor progression, with or without compressive symptoms, is a potential risk.

Neutropenia has been observed in a small number of patients with CD receiving osilodrostat. Preliminary assessment suggests that these events might be associated with cortisol levels that are either below normal or have had a rapid and substantial decline from baseline. In the observed cases, neutropenia rapidly reverses either spontaneously (typically after dose decrease) or with discontinuation of osilodrostat.

In addition, the protocol provides specific guidance for safety follow-up for liver toxicity (increased transaminases, increased total bilirubin) and an algorithm for monitoring and management of QT prolongation.

Conclusion

The treatment of patients with CS still represents a challenge: the available treatments do not lead to biochemical control in quite a large number of patients and many of them lose biochemical control over time.

Therefore there is an unmet medical need to develop new drugs with improved safety, efficacy and a more patient-friendly profile.

Based on current safety and efficacy data of osilodrostat, the overall benefit-risk of trial participation is expected to be positive for all subjects to be enrolled in this study.

5 Population

The investigator or designee must ensure that only patients who meet all the following inclusion and none of the exclusion criteria are offered treatment in the study.

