- Dose Reduced/increased
- Drug interrupted/withdrawn

6. its outcome i.e., its recovery status or whether it was fatal

If the event worsens the event should be reported a second time in the CRF noting the start date when the event worsens in toxicity. For grade 3 and 4 adverse events only, if improvement to a lower grade is determined a new entry for this event should be reported in the CRF noting the start date when the event improved from having been Grade 3 or Grade 4.

Conditions that were already present at the time of informed consent should be recorded in medical history of the subject.

Adverse events (including lab abnormalities that constitute AEs) should be described using a diagnosis whenever possible, rather than individual underlying signs and symptoms.

Adverse event monitoring should be continued for at least 30 days following the last dose of study treatment.

Information about adverse drug reactions for the investigational drug can be found in the Investigator Brochure (IB).

Abnormal laboratory values or test results constitute adverse events only if they fulfill at least one of the following criteria:

- they induce clinical signs or symptoms

- they are considered clinically significant
- they require therapy

Clinically significant abnormal laboratory values or test results must be identified through a review of values outside of normal ranges/clinically notable ranges, significant changes from baseline or the previous visit, or values which are considered to be non-typical in subjects with the underlying disease.

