### 4.1 DATA ANALYSIS GENERAL INFORMATION

The statistical analysis of these data will be performed in accordance with the data analysis section, Section 10, of the study protocol which is available in [Appendix 16.1.1 of the CSR]. Important information is given in the following sections and details are provided, as applicable, in [Appendix 16.1.9 of the CSR].

In summary and analysis tables of continuous variables, standard descriptive statistics (N, mean, standard deviation [SD], median, minimum and maximum) will be presented. The minimum and maximum statistics will be presented in summary tables to the same number of significant figures as the original data. The mean, median, will be presented to one more significant figure than the original data, while SD will be presented to an additional significant figure. For derived variables one figure will be presented for mean, median, minimum, maximum and 25th and 75th percentiles (where requested) and two figures for SD.

In summary tables of categorical variables, the number of non-missing observations by category will be presented with percentages. All percentages will be presented to one decimal place.

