### 5 VARIABLES AND ENDPOINTS

Objectives and related endpoints are described in [Table 5-1](#) below altogether with the planned analysis of collected data.

Study Code: CLCI699C2X01B

Table 5-1 Objectives and related endpoints

Objective	Endpoint	Analysis
Primary		
To evaluate long term safety data, i.e., SAEs and AEs	Frequency and severity of AEs/SAEs	The assessment of safety will be based on the frequency and severity of adverse events (AEs) and serious adverse events (SAEs)
Secondary		
To evaluate clinical benefit as assessed by the investigator	Proportion of patients with clinical benefit as assessed by the investigator at scheduled visits	Proportion of patients with clinical benefit as assessed by the investigator will be summarized at scheduled visits
Other secondary		
To evaluate other safety data and tumor size	Lab parameters, vital signs, ECG, Tumor size and longest dimension	Shift tables vs Baseline and proportions of patients with notable abnormalities or grade 3 or 4

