#### 7.4.3 Vital Signs

All vital signs data (body weight (kg) and systolic/diastolic blood pressure (mmHg)) will be listed by patient and visit/time. Shift tables based on notable values will be provided for vital signs. Change over time from baseline will be summarized.

Vital signs (sitting BP, HR & body weight) reporting of results will include:

- shift table baseline to worst on-treatment result
- table with descriptive statistics at baseline, one or several post-baseline time points and change from baseline to this/these post-baseline time points.

Notable Values for vital signs will include:

- Systolic blood pressure [mmHg] at baseline:  $>=180$  mmHg /  $<=90$  mmHg -
- Diastolic blood pressure [mmHg] at baseline:  $>=105$  mmHg /  $<=50$  mmHg

Notably abnormal vital signs on treatment:

- Systolic blood pressure [mmHg] on treatment:  $>=180$  mmHg with increase from baseline of  $>=20$  mmHg /  $<=90$  mmHg with decrease from baseline of  $>=20$  mmHg;
- Diastolic blood pressure [mmHg] on treatment:  $>=105$  mmHg with increase from baseline of  $>=15$  mmHg/ $<=50$  mmHg with decrease from baseline of  $>=15$  mmHg;

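### SAP Table 5-1 promises shift tables and notable-abnormality proportions for tumour size, but SAP 7.4.5 defines no notable tumour change, so no MRI-based output counts the patients whose tumour grew

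*SAP*

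**What the plan says.** - **SAP Table 5-1, other secondary objective.** One row holds "Lab parameters, vital signs, ECG, Tumor size and longest dimension". The analysis given for the whole row is "Shift tables vs Baseline and proportions of patients with notable abnormalities or grade 3 or 4". Tumour measurements are not excepted.
- **SAP 7.4.5.** For volume, a "descriptive summary of actual tumor volumes as well as its change from baseline will be provided at visits where evaluation is scheduled". Where an image cannot be read for volume, "the longest dimension (in mm) will be summarized instead". Nothing further is specified.
- **SAP 4.1.** For continuous variables, "standard descriptive statistics (N, mean, standard deviation [SD], median, minimum and maximum) will be presented".
- **Protocol 2, Table 2-1.** The secondary safety endpoint covers the frequency and severity of safety assessments as well as summaries of them, and pituitary MRI is one of the assessments.
- **Protocol 12.5.1.4.** Tumour volume and longest dimension are to be listed and summarised; the specific analyses are left to the SAP.
- **Protocol 4.5.** "Corticotroph tumor progression, with or without compressive symptoms, is a potential risk".
- **Adverse event outputs.** SAP 2.3 (interim) and 7.4.1 (final), with attachment 8.1, provide for a special-interest category of events related to pituitary tumour enlargement.

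**The concern.** Tumour growth happens in individual patients, so the natural safety question is how many patients' tumours grew, and by how much. Table 5-1 promises an answer of that kind, but the section that should deliver it never says what counts as a notable tumour change. A programmer would have to invent the category, possibly after seeing the data, or leave the output out.

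At stake is how a named potential risk is described. The planned table can show a mean and median change close to zero while several small tumours have doubled. The adverse event route is filtered by judgement: "Abnormal laboratory values or test results constitute adverse events only if they fulfill at least one of the following criteria", namely signs or symptoms, clinical significance, or a need for therapy.

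**Working it through.** The plan has no figure to reproduce: no sample size is calculated and no hypothesis is tested. The check is a comparison of text, followed by illustrations on assumed inputs.

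**1. Does each parameter in the Table 5-1 row have a per-patient rule?**

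| Parameter | SAP section | Rule |
|---|---|---|
| Laboratory | 7.4.2 | CTCAE grades or low/normal/high; shift tables; grade 3 or 4 |
| Vital signs | 7.4.3 | "Shift tables based on notable values will be provided for vital signs"; limits for blood pressure and weight |
| ECG | 7.4.4 | Limits for PR, QRS, QT/QTcF and heart rate; number and percentage of patients |
| Tumour | 7.4.5 | None |

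**2. Can the count be recovered from the descriptive summary?** Three invented sets of 100 changes were built. Each has one value of +60, 52 zeros and one of -20. The rest are:

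- 8 increases: seven at +24.35 and 39 at -1.55. Sum = 60 + 170.45 - 20 - 60.45 = 150.
- 24 increases: 23 at +11.69 and 23 at -6.91. Sum, before rounding of the values, = 150.
- 40 increases: 39 at +6.33 and seven at -19.57. Sum, before rounding of the values, = 150.

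All three have mean 1.5, SD 9.0, median 0, minimum -20 and maximum 60. The summary does not fix the count.

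**3. Would the average show growth in small tumours?** Assumed inputs, none from the documents: 100 patients with a measurable tumour, 80 of 6 mm and 20 of either 14 or 20 mm; log-normal read error with CV 10-20% on each scan; eight small tumours truly doubling; change taken as a difference in mm3.

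- Sphere volume = (pi/6) x d^3, giving 113, 1,437 and 4,189 mm3.
- Expected mean change = 8 x 113 / 100 = about 9 mm3.
- Simulated standard error (5,000 trials per setting): 9-19 mm3 with 14 mm tumours, 26-54 mm3 with 20 mm tumours. Median change: 2-4 mm3.

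The signal is at or below the noise contributed by a few large tumours.

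**4. How does a per-patient count behave?** With one follow-up scan and log-scale SD s = sqrt(ln(1 + CV^2)), the chance that an unchanged tumour shows a ratio of at least k is 1 - Phi(ln k / (s x sqrt 2)).

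- CV 10%: s x sqrt 2 = 0.141. For k = 1.5, z = 0.405/0.141 = 2.87, or 0.2 per 100. For k = 2, about 0.
- CV 20%: s x sqrt 2 = 0.280. For k = 1.5, z = 0.405/0.280 = 1.45, or 7.4 per 100. For k = 2, z = 0.693/0.280 = 2.47, or 0.7 per 100.

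With eight true doublings the expected counts are 8.0-13.6 (at least 50%) and 4.0-4.6 (at least 100%). A tumour that exactly doubles passes the 100% cut only half the time (8 x 0.5 = 4), which is why a 50% row is useful as support.

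**5. Which scan should be counted?** Protocol 8.4.6 schedules MRI every 48 weeks and the study is open for about 5 years: 5 x 365.25 / 7 / 48 = 5.4, so up to about five follow-up scans. False counts per 100 patients with no true growth, by simulation:

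| Rule | At least 50% | At least 100% |
|---|---|---|
| One scan, CV 10-20% | 0.2-7.4 | 0-0.7 |
| Largest of five, CV 10-20% | 0.9-23 | 0-2.7 |

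At CV 15% the largest-of-five count at 50% is about 10. At CV 20%, eight true doublings give about 29 against 23 with none, so a largest-increase rule at 50% would report mostly read error.

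**6. Longest dimension only.** The spherical equivalent of doubling is 2^(1/3) = 1.26. A 1 mm read difference reaches 26% in tumours up to 1/0.26 = 3.8 mm, and 2 mm in tumours up to 7.7 mm.

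**The case against.** A reader might infer that no planned output says anything about how many tumours grew. The documents do not support that:

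- The special-interest category counts patients with reported events, and its terms include pituitary enlargement and neoplasm progression.
- Protocol 10.1.1 asks for significant changes from baseline or from the previous visit to be reviewed when judging clinical significance. Protocol 9.1.1 lists certain tumour growth among the adverse events that require discontinuation, so that growth would also reach the discontinuation outputs.
- Protocol 12.5.1.4 provides a listing from which growth could be counted by hand.

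All of this stands, and the most consequential growth should be visible. It does not replace a measured count. The adverse event category depends on reporting and also contains diplopia, cranial nerve injury and apoplexy. A hand count from the listing would use a threshold chosen after the data are seen.

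A reader might also infer that 7.4.5 restricts itself to absolute change. It says only change from baseline, so percent change is unspecified rather than excluded. Step 3 depends on the absolute reading; steps 1 and 2 do not.

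The illustrations rest on invented sizes, read error and growth. The documents report 100 patients enrolled by 8 April 2020, but entry is open to any endogenous Cushing's syndrome and one osilodrostat study named in the protocol excludes Cushing's disease, so fewer may have a measurable pituitary tumour. Because nothing is tested, whether a confidence interval covers zero has little bearing.

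Finally, the conflict could be removed by taking tumour size out of the Table 5-1 row. That would reconcile the text but leave measured growth uncounted.

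**Conclusion.** The point holds as a mismatch within the SAP. Table 5-1 promises a categorical, per-patient analysis of tumour size; 7.4.5 supplies no category, and the planned statistics cannot yield one. The missing item is specifically an MRI-based count of patients with growth. Enlargement reported as an adverse event is counted, and individual measurements are to be listed.

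That conclusion needs no assumed numbers. The size of what could be missed does: under the inputs in step 3, eight doublings among 100 patients move the mean by about 9 mm3 against a standard error of 9-54 mm3. The false-count figures also assume independent read error across scans and up to five scans per patient; fewer scans would reduce them.

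This affects a descriptive secondary safety endpoint, not the primary one. It should be corrected before the final tables are produced.

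**What to change.** In SAP 7.4.5, for patients with a measurable baseline tumour and at least one later scan:

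- Show percent change beside change in the by-visit table.
- Report n/N (%) of evaluable patients with a volume increase of at least 100%, with at least 50% as a supportive row, at each scheduled scan and at the last available scan. Do not use the largest of repeated scans.
- If a worst-value row is kept, require the increase on two consecutive scans or at the last scan. Two consecutive scans must give no more false counts than any one of five, although error in the shared baseline reading remains.
- Put patients with longest dimension only in a separate row (at least 26%), with a note that a 1-2 mm read difference can reach it in small tumours.
- Count separately tumours first visible after baseline.
- Name these rows in Table 5-1 as the tumour notable abnormality.

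The cost is SAP wording and one table, from data already in the eCRF and the parent-study transfer (SAP 5.3). No assessment is added. The downside is that the cut-offs are conventional, local read error will give some false counts, and a strict 100% cut misses about half of exact doublings. The table should say so.
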